3.4.2 Secondary study outcomes

Secondary outcomes of the study include:

For Cohorts 1 and 3 :

- The longitudinal prevalence of :
 - Wasting, defined as above (cohort 3)
 - MAM, defined for each child as the number of MAM diagnoses divided by the total number of monthly visits made
 - SAM, defined for each child as the number of SAM diagnoses divided by the total number of monthly visits made
- The incidence of :
 - Wasting, defined as above (cohort 1).
 - MAM, defined as the number of new MAM cases recorded during monthly visits.
 - SAM, defined as the number of new SAM cases recorded during monthly visits.
- The prevalence of anemia defined as the proportion of children with a hemoglobin level below 11g/dl at the end of the study.
- Mean hemoglobin concentration at the end of the study.
- Prevalence of stunting defined as the proportion of children with HAZ <-2 (relative to the 2006 WHO reference) at the end of the study.
- The average z-scores HAZ at the end of the study.
- Wasting screening coverage defined as the proportion of children screened (using MUAC, weight-for-height or bilateral edema) in the month prior to the monthly visit. Two sub-outcomes will also be considered:
 - Screening coverage by care groups.
 - Screening coverage of the family MUAC component, which is the screening performed by a family member in the past month.
- Linear growth rate defined as the change in height-for-age index per month.
- Speed of weight growth defined as the change in weight-for-height index per month.
- Weight gain defined as the weight change per month.
- MUAC gain defined as the change in MUAC per month.

- The longitudinal prevalence of childhood morbidity, i.e. acute respiratory infections, fever, diarrhea and malaria, defined as the number of reports of signs of these morbidities divided by the total number of days reported (1-3 per monthly visit made).
- Mother/guardian's knowledge of nutrition, WASH, and health expressed as cumulative total and domain scores at exit.
- Infant and young child feeding (IYCF) practices:
 - Introduction of (semi) solid and soft complementary foods .
 - Minimum dietary diversity in children, defined as the proportion of children who consumed at least 5 of the 8 food groups (including breast milk) the day before the survey.

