3.5 Sample Size

3.5.1 Cohort 1 – primary outcome: longitudinal prevalence of wasting

The main cohort (#1) will include 1,750 children in the community aged 6 to 6.9 months, included for a period of 7 months and followed up monthly until the end of the study (total duration: 9 months).

The main cohort (#1) will include children aged 6-6.9 months. Given the small size of most villages and the sample size needed to detect a significant, plausible and meaningful difference in longitudinal wasting prevalence (primary outcome) between groups, we have calculated that we need to include an average of 3 children per month for 7 months in the 50 largest villages (25 villages in the control group and 25 in the intervention group) and an average of 2 children per month for 7 months in the 50 smallest villages in the study area (i.e., the medium-sized villages in the Mongo Health District: equally 25 in the control group and 25 in the intervention group). The children will all leave the cohort in the same month: counting the month of inclusion, the children will be seen for a maximum of 9 months (for children included at the start of the study) and a minimum of 3 months (for children included during the 7th month). This will result in a total sample of 1,750 children (10,500 visits in total of which 1,750 inclusions and 8,750 follow-ups). With 15% dropout, **the size of this study would provide sufficient power to detect a relative decrease of about 35% in the longitudinal prevalence of wasting**, with a power of 80% and a statistical significance of 5%, taking into account the cluster effect at the village level and the imbalance in cluster size.

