Exclusion criteria	Congenital malformations that make anthropometric measurements impossible. Mother intends to leave the study area by December 2021.	None.	Congenital malformations that make anthropometric measurements impossible. Mother intends to leave the study area by December 2021.
Sample size	1,750 children	Exhaustive inclusion	700 children
Intended duration of inclusion	7 months	9 months	2 months
Follow-up frequency	Monthly	Bi-monthly visit by enumerators to health center treatment units, and monthly visits to community treatment units.	Monthly
Intended study duration	enrolled children will be followed until the end of the study, with a total study duration of 9 months	from program admission to program exit, with a total study duration of 9 months.	Follow-up of all children for 6 months, with a total study duration of 8 months.
Changes to the protocol	November 2021: Study duration was increased by a month and exits were split evenly across the 2 last months of the study, based on enrollment order.	November 2021: Study duration was increased by a month.	November 2021: To meet the sample size, we extended the inclusion duration to 7 months January 2022: To meet the sample size, we extended the inclusion duration to 9 months, and we released the limitation on the maximum number of children per village. We also extended the total study to 12 months, and enrolled children will be followed-up either for 6 months, or until the end of the study, whatever comes first.

4 Data management

The management of all research data will follow IFPRI's institutional research data management protocol, overseen by the IFPRI Data Governance Committee, as well as UNICEF data governance standards. All received data will be carefully anonymized and de-identified so that the privacy of participants and research subjects is fully protected. Personally Identifiable Information data (PII; names, telephone

numbers, GPS coordinates, date of birth) will be stripped from the research data when receiving the data on the server. During data collection, PII data will be stored in a separate secured server folder accessible only to the Principal Investigators. PII data will only be used to identify a household to conduct additional verification of previously collected data. When data collection and data validation have been completed, PII data will be destroyed.

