6.1 Guiding principles and analysis strategy

Data will be analyzed on intent-to-treat basis. To allow for an analysis “as randomized” in the presence of missing data, we will impute missing data of the primary outcomes of the longitudinal study using a multiple imputation strategy under the *missing at random* assumption (see section 6.3 below). Data management, data cleaning, and statistical analyses will be done using Stata 17.0 (Statacorp, USA). The statistical significance will be set at 5%. All statistical tests will be two-sided. The analysis of primary study outcomes will not be adjusted for multiple testing (n=3 primary study outcomes) given the data involved represent three distinct experimental and control study samples with each one primary study outcome.

We will present results from non-adjusted and adjusted linear mixed effects regression models.

The non-adjusted models to analyze cohort 1 and 3 data will use *village (cluster)* as a random intercept and sampling stratum as a fixed effect to represent the study design. The non-adjusted models to analyze cohort 2 data will include sampling stratum as a fixed effect and will use a random intercept at the health center level and a random slope at the village level, to account for nesting of villages (clusters) into health centers (where treatment occurs for children from several villages).

In addition, we will conduct adjusted analyses, adjusting for the following variables:

- covariates that appear imbalanced at enrollment (absolute difference >10 pp) and are unlikely to have been impacted by exposure to the intervention before 6 months of age (cohort 1 and 3; virtually no household, parental or sociodemographic child level data collected at admission in cohort 2).
- child sex, and whether child was the first live birth, since a recent meta-analysis has reported that imbalance in child nutritional status between study groups can be associated to the imbalance in child sex and primiparity (3) (all adjusted models, except that data on first live birth are missing for cohort 2).
- month of enrollment (longitudinal models, cohorts 1 and 3) or month of admission into treatment (cohort 2).
- Child age at enrollment (cohort 3; constant in cohort 1; not detailed in MAM treatment registers used for cohort 2).
- type of nutrition unit where the child is/was treated (cohorts 2 and 3).

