6.4 Impact assessments

6.4.1 Main analyses

Impact on wasting longitudinal prevalence (primary outcome of cohort 1), wasting incidence (primary outcome of cohort 3), MAM and SAM longitudinal prevalence and incidence, and morbidity longitudinal prevalence, will be estimated using a mixed effects Poisson regression model with robust estimation of standard errors.

For other longitudinal outcomes, we will use linear mixed-effects regression models to assess the impact of the intervention on continuous outcomes and linear probability mixed-effects regression models with robust estimation of standard errors to assess the impact of the intervention on binary outcomes (19). Repeated visits within a child in longitudinal models will be accounted for by including a random intercept at the child level and a random slope at the visit level (defined as number of months since enrollment). For longitudinal models with continuous anthropometric outcomes (growth curves analyses), we will assess if the addition of a quadratic term of time (visit) improves the model fit significantly by applying a likelihood ratio test comparing the model with and without the quadratic term. To assess the specific

⁶ De Silva AP, Moreno-Betancur M, De Livera AM, Lee KJ, Simpson JA. (2017) A comparison of multiple imputation methods for handling missing values in longitudinal data in the presence of a time-varying covariate with a non-linear association with time: A simulation study. *BMC Med Res Methodol*; 17:1–11

impact of the intervention from enrollment at the age of 6 months to the end of follow-up, we will assess the interaction between intervention allocation and time (visit).

For cross-sectional analyses on outcomes measured at exit from cohorts 1 and 3 (mainly cumulative outcomes such as knowledge, vaccination, stunting, etc...) and on cohort 2 outcomes, we will use linear probability mixed-effects regression models with robust estimation of standard errors to assess the impact of the intervention on binary outcomes (including recovery rate, primary outcome of cohort 2), and linear mixed-effects regression models to assess impacts on continuous outcomes (19).

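### Adjusted exit models for haemoglobin, anaemia, HAZ and stunting omit month of enrolment and follow-up time: a small precision loss in cohort 1, a modest open risk in cohort 3

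*SAP*

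**What the plan says.** SAP 6.1 presents unadjusted and adjusted models. One adjustment variable is "month of enrollment (longitudinal models, cohorts 1 and 3) or month of admission into treatment (cohort 2". Another is "Child age at enrollment (cohort 3; constant in cohort 1; not detailed in MAM treatment registers used for cohort 2"; this age term is not limited to any model type.

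SAP 6.4.1 deals with longitudinal outcomes first and then, in its own paragraph, with exit outcomes: "For cross-sectional analyses on outcomes measured at exit from cohorts 1 and 3 (mainly cumulative outcomes such as knowledge, vaccination, stunting, etc". SAP 3.4.2 defines the outcomes at issue at study end, for example "Mean hemoglobin concentration at the end of the study" and "The average z-scores HAZ at the end of the study", together with anaemia and stunting prevalence. SAP 6.2.2 rules out adjusting exit analyses for the enrolment value of the outcome, because children may already have been exposed to the programme by then.

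On timing, SAP 3.5.1 says of cohort 1 that "the children will be seen for a maximum of 9 months" and for no fewer than 3, counting the inclusion month. Table 2 in SAP 3.6 then records the November 2021 change: one more study month, with cohort 1 exits divided between the last two months by order of enrolment. For cohort 3 it records the January 2022 change: inclusion over 9 months, a total duration of 12 months, and "enrolled children will be followed-up either for 6 months, or until the end of the study, whatever comes first".

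**The concern.** Because the month term is tied to longitudinal models and exit outcomes are a separate class, the adjusted exit models of cohorts 1 and 3 have nothing that represents when a child entered or how long the child was followed. Enrolment month is not among the Table 3 characteristics either, so the imbalance rule in SAP 6.1 would not bring it in.

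Haemoglobin and HAZ can be expected to move with age, season and time since entry. In cohort 1, age is constant at enrolment only, so the spread in time to exit becomes unexplained variation. In cohort 3 more is at stake. SAP 3.2 says the randomised character of the comparison is not fully guaranteed, and the intervention acts on screening, referral and adherence, hence possibly on when children are discharged and enrolled. Follow-up is now cut off at study end, so an arm difference in enrolment timing becomes an arm difference in follow-up length and exit season.

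Haemoglobin is the clearest case. It is measured only at enrolment and exit (SAP 5.1), so no monthly growth-curve analysis stands behind it, as one does for HAZ.

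**Working it through.** **1. The plan's own count.** Children: 50×3×7 + 50×2×7 = 1,750, or 250 per inclusion month. Visits: 250×(9+8+7+6+5+4+3) = 10,500, of which 10,500 − 1,750 = 8,750 are follow-ups. This matches SAP 3.5.1 and confirms the planned spread of 9 down to 3 visits.

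**2. Cohort 1, time from enrolment to exit.**
- Original calendar, all exits in month 9: 9 − m for m = 1 to 7 gives 8, 7, 6, 5, 4, 3, 2. Mean 5.0, variance 4.0, SD 2.0. Exit age is about 8 to 15 months.
- Current schedule (10 months; earlier-enrolled half exits in month 9, later half in month 10; order assumed to apply across the whole cohort): 8, 7, 6, then 5 or 6 (half each), 5, 4, 3. Mean 5.5, variance 17.75/7 = 2.54, SD 1.59. Exit age is about 9 to 15 months.

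**3. Cohort 1, cost of omission.** Variance share R² = slope² × Var(time) / SD². Standard error inflation = 1/√(1 − R²) − 1. The documents give no slopes or outcome SDs, so the ranges below are assumptions.

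| Outcome | Assumed slope per month | Assumed SD | Inflation, current schedule | Inflation, original calendar |
|---|---|---|---|---|
| HAZ | 0.03–0.10 z | 1.1–1.3 | 0.07–1.06% | 0.11–1.70% |
| Haemoglobin | 0.02–0.10 g/dL | 1.2–1.5 | 0.02–0.89% | 0.04–1.42% |

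Example (HAZ, current schedule): 0.10² × 2.54 / 1.1² = 0.021; 1/√0.979 − 1 = 1.06%.

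**4. Cohort 3, follow-up length.** Follow-up = min(6, 12 − m) for inclusion month m = 1 to 9: six months for m = 1 to 6, then 5, 4 and 3. With even enrolment the mean is 48/9 = 5.33, the variance 10/9 = 1.11 and the SD 1.05.

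**5. Cohort 3, what the age term already covers.** If age at enrolment is uniform over 6 to 24 months (assumption), its variance is 18²/12 = 27.0. Its share of exit-age variance is 27.0/(27.0 + 1.11) = 96%. Follow-up length and calendar month of exit remain uncontrolled.

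**6. Cohort 3, possible bias.** Children included in months 7 to 9 average (5+4+3)/3 = 4 months of follow-up, against 6 for the rest. If the share enrolled late differs between arms by s, mean follow-up differs by 2s. Bias = slope × 2s.
- s = 10 points: 0.2 month; HAZ 0.006–0.02 z; haemoglobin 0.004–0.02 g/dL.
- s = 30 points: 0.6 month; HAZ 0.018–0.06 z; haemoglobin 0.012–0.06 g/dL.

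For scale, the standard error of the HAZ difference uses assumed SD 1.2, 15% loss and ICC 0 to 0.05. With n = 350×0.85 = 297.5 per arm and 7×0.85 = 5.95 per cluster, it is 1.2×√(2×[1 + 4.95×ICC]/297.5) = 0.098 to 0.110.

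**The case against.** The strongest reply is that little is left once the plan is read in full. In cohort 1, clusters are randomised and planned monthly intake is the same in both arms for villages of a given size, so no bias is expected. The current exit schedule also narrows the spread (SD 2.0 down to about 1.6), and growth in HAZ is modelled longitudinally as well. In cohort 3, the SAP acknowledges the quasi-experimental design, asks for caution, tests enrolment differences and adjusts for age at enrolment and type of nutrition unit. All of this stands, and it keeps the point small.

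Three stronger readings are tempting but not supported.
- A reader might infer that the exit models have no age term at all. That is true of cohort 1 only; the adjusted cohort 3 models include age at enrolment, which covers most of the variation in exit age.
- A reader might take from SAP 3.5.1 that cohort 1 children all leave in the same month. Table 2 replaced that arrangement.
- A reader might suppose an arm gap of 0.5 to 1 month in cohort 3 follow-up. By step 6 that needs a 25 to 50 point difference in late enrolment, and nothing in the documents points to one.

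A further objection is that cohort 3 enrolment timing may itself be affected by the intervention, so conditioning on it is not innocent. That is fair, but the SAP already accepts this adjustment in its cohort 3 longitudinal models. It also adjusts cohort 2 outcomes, which fall in the same cross-sectional paragraph, for month of admission. No reason is given for treating the exit models differently.

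**Conclusion.** The omission is real and its consequences are small. In cohort 1 it costs about 0 to 1% of the standard error under the current schedule, up to about 2% on the original calendar, with no expected bias. In cohort 3 it leaves the exit comparison open to arm differences in follow-up length and season. Under a 10 to 30 point difference in late enrolment this is about 0.01 to 0.06 HAZ z, at most a little over half of a standard error of 0.10 to 0.11.

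These sizes rest on assumed slopes, SDs, ICCs and enrolment differences. A seasonal effect on haemoglobin would be additional and cannot be sized from the documents. Only secondary outcomes are affected, so this is a worthwhile refinement and no threat to the trial's main conclusions.

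**What to change.** In SAP 6.1, remove the restriction to longitudinal models so that month of enrolment also enters the adjusted exit models of cohorts 1 and 3, preferably as monthly indicators.

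- **Cohort 1:** this stands in for age at exit. The two are nearly collinear, so one suffices.
- **Cohort 3:** monthly indicators also capture planned follow-up length, since that is a function of inclusion month (step 4). Report mean time from enrolment to exit by arm, which will show whether the risk materialised and will help in reading the unadjusted results.
- **Optional:** repeat the cohort 3 exit analysis in children with the full 6 months, labelled as a sensitivity analysis because enrolment timing may be affected by the intervention.

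The cost is one line of text, a few model terms and one descriptive row. The dates needed are already collected.

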6.2 Enrollment characteristics

6.2.1 Characteristics of study groups at enrollment

The presentation of enrollment characteristics (see Table 3) will be done as follows:

- Categorical variables: frequencies and percentages, as appropriate. Percentages will be calculated based on the number of participants for whom data are available.
- Continuous variables: mean and SD or median and interquartile range, as appropriate.

Following the CONSORT guidelines, we will not statistically test for differences between study groups at enrollment in cohort 1 (18). Imbalance will be considered for absolute differences >10 pp (binary

outcomes) or >10 % (continuous outcomes). However, as the intervention risks impacting the size and characteristics of the study population for cohort 3 (if it impacts who is wasted, and then treated and cured from wasting), we will test baseline differences across groups in cohort 3, using linear (continuous outcomes) and linear probability (binary outcomes) mixed-effects regression models with robust estimation of standard errors, considering the cluster as a random effect, and strata and intervention as a fixed effect.

Table 3: Enrollment characteristics for cohorts 1 and 3

Characteristics	Comments/References
Household level	
HH size (mean/SD)	
Number of under 5 children in household (mean/SD)	
Number of adults (15-64 y) (mean/SD)	
Polygamous HH(%)	
HH food insecurity (mean and proportion of food secure HH)	Coates J, Swindale A, Bilinsky P. Household Food Insecurity Access Scale (HFIAS) for measurement of food access: indicator guide. Washington, DC: FANTA; 2007. https://doi.org/10.1007/s13398-014-0173-7.2
SES status classification (tertiles, %)	Principal component analysis will be used to construct a proxy household Socio-Economic Score (SES) using ownership of various assets (an asset is excluded if ownership is below 5% or above 95% on HH level), housing materials, primary source of lighting, primary energy source, and home ownership. Tertiles of the first principal component (i.e., the one with the highest eigenvalue) will be used.
Improved water treatment technologies used (%)	USAID (2021) Water and development- Indicator handbook. Washington DC
Improved sanitation facility (%)	USAID (2021) Water and development- Indicator handbook. Washington DC
Handwashing station with soap available (%)	USAID (2021) Water and development- Indicator handbook. Washington DC
Improved primary water source (%)	USAID (2021) Water and development- Indicator handbook. Washington DC
Distance to nearest health center, km	Linear distance between households and the nearest health center calculated using Global Position System coordinates
Distance to nearest wasting treatment unit, km	Linear distance between households and the nearest wasting treatment unit (health center or treatment unit in the community)
Household head level	
Male head of household (%)	
Adult (15-64 years) (%)	
Elderly (65+ years) (%)	
Paternal level	
Father is head of HH (%)	

Characteristics	Comments/References
Age (mean/SD)	
Male (%)	
Head of household school attendance	
Has an income generating activity (%)	
Parental confidence scale	Črnčec R, Barnett B, Matthey S. Development of an instrument to assess perceived self-efficacy in the parents of infants. Res Nurs Health. Res Nurs Health; 2008
Severe clinical range (less than 31)	
Moderate clinical range (31-35)	
Maternal	
Biological mother (%)	
Age (mean/SD)	
Spouse of head of household (%)	
School attendance (Never attended school, %)	
Has an income generating activity (%)	
Height (meand/SD)	
Possible depression (EPDS \geq 10)	Cox JL, Chapman G, Murray D, Jones P. Validation of the Edinburgh postnatal depression scale (EPDS) in non-postnatal women. J Affect Disord ; 1996;39:185–9.
Parental confidence scale	Črnčec R, Barnett B, Matthey S. Development of an instrument to assess perceived self-efficacy in the parents of infants. Res Nurs Health. Res Nurs Health; 2008; 31:442–53.
Severe clinical range (less than 31)	
Moderate clinical range (31-35)	
Number of food groups consumed over last 24h (mean/SD)	Out of a maximum of 10 food groups as proposed by Martin-Prevel Y, Allemand P, Wiesmann D, Arimond M, Ballard T, Deitchler M, et al. Moving forward on choosing a standard operational indicator of women's dietary diversity. Rome: FAO; 2015. Food groups are starchy staple foods, nuts and seeds, flesh foods, dark green leafy vegetables, pulses, dairy, eggs, vitamin A rich fruits and vegetables, other vegetables and other fruits
Minimum dietary diversity (having consumed at least 5 of 10 food groups during the last 24h)	Martin-Prevel Y, Allemand P, Wiesmann D, Arimond M, Ballard T, Deitchler M, et al. Moving forward on choosing a standard operational indicator of women's dietary diversity. Rome: FAO; 2015
Body Mass index (kg.m $^{-2}$) (mean/SD)	
Underweight (BMI $<$ 18.5) (mean/SD)	

Characteristics	Comments/References
Assisted delivery of last pregnancy (%)	
Number of antenatal consultations attended during last pregnancy (%)	
Breastfeeding, complementary feeding, health and hygiene, MUAC screening, CMAM knowledge score (mean/SD)	Self-developed questionnaire based on training curricula for GSAN. Mean scores are presented by domain, as well as an overall score based on the 36 questions
Child	
Age (mean/SD)	
Male (%)	
Primiparity	
Introduction of (semi)solid and soft foods (%)	
Minimum dietary diversity (%)	Indicators for assessing infant and young child feeding practices: definitions and measurement methods. Geneva: World Health Organization and the United Nations Children's Fund (UNICEF), 2021
Minimum meal frequency(%)	
Minimum acceptable diet(%)	
Consumption of iron-rich or iron-fortified foods (%)	
Hemoglobin concentration (hb) (%)	As measured by hemocue 301
Anemia (hb<11 g/dl)	
Severe anemia (hb<7 g/dl)	
Weight-for-length Z-score (mean/SD)	Relative to WHO 2006 growth reference
MUAC (mean/SD)	
Wasting (WLZ<-2 or MUAC<125mm or edema)	
Severe Acute malnutrition (WLZ<-3 or MUAC<115mm or edema)	
Length-for-age Z-score (mean/SD)	Relative to WHO 2006 growth reference
Stunting (LAZ<-2)	
Weight-for-age Z-score (mean/SD)	Relative to WHO 2006 growth reference
Underweight (WAZ<-2)	

